6.7. Intervention After the End of the Study

No intervention will be provided to study participants after the end of the study.

7. DISCONTINUATION OF STUDY INTERVENTION AND PARTICIPANT DISCONTINUATION/WITHDRAWAL

7.1. Discontinuation of Study Intervention

In rare instances, it may be necessary for a participant to permanently discontinue study intervention (definitive discontinuation). Reasons for definitive discontinuation of study intervention include (but are not limited to) the following: AEs, Physician decision, withdrawal by participants.

Note that discontinuation of study intervention does not represent withdrawal from the study. If study intervention is definitively discontinued, the participant will remain in the study to be evaluated for safety and other assessments. See the [SoA](#) for data to be collected at the time of discontinuation of study intervention and follow-up for any further evaluations that need to be completed.

In the event of discontinuation of study intervention, it must be documented on the appropriate CRF/in the medical records whether the participant is discontinuing further receipt of study intervention or also from study procedures, posttreatment study follow-up, and/or future collection of additional information.

At the discretion of the Investigator, in the event of a significant safety concern such as changes in renal or cardiac function, infusion of the study intervention may be interrupted or terminated.

If anaphylaxis or a serious allergic reaction is noted, the study intervention should be immediately stopped, and the participant should be discontinued. Additionally, other adverse events or confirmed laboratory abnormalities judged by the investigator to be a significant safety concern should also lead to immediate stop to study intervention.

The Sponsor, in consultation with the independent IRC and/or a competent regulatory agency, may also mandate discontinuation based on review of PK or safety data.

If a participant discontinues study intervention, he/she should complete the “Early Termination” visit ([SoA](#)).

In addition, intervention will be discontinued for the following changes in ECG.

ECG Changes

A participant who meets either bulleted criteria based on the average of triplicate ECG readings that are deemed to be related to the administration of PF-07304814 will be withdrawn from the study intervention.

- QTcF >500 msec.
- Change from baseline: QTcF >60 msec.

If a clinically significant finding is identified (including, but not limited to, changes from baseline in QTcF after enrolment), the investigator or qualified designee will determine if the participant can continue in the study and if any change in participant management is needed. This review of the ECG printed at the time of collection must be documented. Any new clinically relevant finding should be reported as an AE.

7.1.1. Temporary Discontinuation

In **Part 1: SAD**, if infusion is temporary interrupted, it should be resumed as soon as possible and the complete dose should be administered. Temporary discontinuation for longer than 2 hours is not permitted. Participants may temporarily discontinue from **Part 2: MAD** for up to 6 hours over the 120-h infusion period (if possible, each interruption should be no longer than 2 hours) to reduce risk to the participant at the discretion of the investigator. If study intervention administration is restarted the remaining course will be given. Temporary discontinuation for longer than 6 hours is not permitted.

7.1.2. Rechallenge

Not applicable.

7.2. Participant Discontinuation/Withdrawal From the Study

A participant may withdraw from the study at any time at his/her own request. Reasons for discontinuation from the study include the following:

- Refused further follow-up;
- Lost to follow-up;
- Death;
- Physician decision;
- Pregnancy;
- Study terminated by sponsor.

At the time of discontinuing from the study, if possible, an early discontinuation visit should be conducted. See the [SoA](#) for assessments to be collected at the time of study discontinuation and follow-up and for any further evaluations that need to be completed.

The early discontinuation visit applies only to participants who are enrolled/randomized and then are prematurely withdrawn from the study. Participants should be questioned regarding their reason for withdrawal.

The participant will be permanently discontinued both from the study intervention and from the study at that time.

If a participant withdraws from the study, he/she may request destruction of any remaining samples taken and not tested, and the investigator must document any such requests in the site study records and notify the sponsor accordingly.

If the participant withdraws from the study and also withdraws consent (see [Section 7.2.1](#)) for disclosure of future information, no further evaluations should be performed and no additional data should be collected. The sponsor may retain and continue to use any data collected before such withdrawal of consent.

Lack of completion of all or any of the withdrawal/early termination procedures will not be viewed as protocol deviations so long as the participant's safety was preserved.

7.2.1. Withdrawal of Consent

Participants who request to discontinue receipt of study intervention will remain in the study and must continue to be followed for protocol-specified follow-up procedures. The only exception to this is when a participant specifically withdraws consent for any further contact with him or her or persons previously authorized by the participant to provide this information. Participants should notify the investigator in writing of the decision to withdraw consent from future follow-up, whenever possible. The withdrawal of consent should be explained in detail in the medical records by the investigator, as to whether the withdrawal is only from further receipt of study intervention or also from study procedures and/or posttreatment study follow-up and entered on the appropriate CRF page. In the event that vital status (whether the participant is alive or dead) is being measured, publicly available information should be used to determine vital status only as appropriately directed in accordance with local law.

7.3. Lost to Follow-up

A participant will be considered lost to follow-up if he or she repeatedly fails to return for scheduled visits and is unable to be contacted by the study site.

The following actions must be taken if a participant fails to attend a required study visit:

- The site must attempt to contact the participant and reschedule the missed visit as soon as possible and counsel the participant on the importance of maintaining the assigned visit schedule and ascertain whether or not the participant wishes to and/or should continue in the study;
- Before a participant is deemed lost to follow-up, the investigator or designee must make every effort to regain contact with the participant (where possible, 3 telephone calls and, if necessary, a certified letter to the participant's last known mailing address or local equivalent methods). These contact attempts should be documented in the participant's medical record;

- Should the participant continue to be unreachable, he/she will be considered to have withdrawn from the study.

8. STUDY ASSESSMENTS AND PROCEDURES

The investigator (or an appropriate delegate at the investigator site) must obtain a signed and dated ICD before performing any study-specific procedures.

Study procedures and their timing are summarized in the [SoA](#). Protocol waivers or exemptions are not allowed.

Safety issues should be discussed with the sponsor immediately upon occurrence or awareness to determine whether the participant should continue or discontinue study intervention.

Adherence to the study design requirements, including those specified in the [SoA](#), is essential and required for study conduct.

All screening evaluations must be completed and reviewed to confirm that potential participants meet all eligibility criteria. The investigator will maintain a screening log to record details of all participants screened and to confirm eligibility or record reasons for screening failure, as applicable.

Procedures conducted as part of the participant's routine clinical management (eg, blood count) and obtained before signing of the ICD may be utilized for screening purposes provided the procedures met the protocol-specified criteria and were performed within the time frame defined in the [SoA](#).

Every effort should be made to ensure that protocol-required tests and procedures are completed as described. However, it is anticipated that from time to time there may be circumstances outside the control of the investigator that may make it unfeasible to perform the test. In these cases, the investigator must take all steps necessary to ensure the safety and well-being of the participant. When a protocol-required test cannot be performed, the investigator will document the reason for the missed test and any corrective and preventive actions that he or she has taken to ensure that required processes are adhered to as soon as possible. The study team must be informed of these incidents in a timely manner.

For samples being collected and shipped, detailed collection, processing, storage, and shipment instructions and contact information will be provided to the investigator site prior to initiation of the study as outlined in the lab manual.

The total blood sampling volume for individual participants in this study is approximately 225 mL in **Part 1: SAD** and 360 mL in **Part 2: MAD**. The actual collection times of blood sampling may change. Additional blood samples may be taken for safety assessments at times specified by Pfizer, provided the total volume taken during the study does not exceed 550 mL during any period of 60 consecutive days.

Note: In order to draw blood samples for safety assessments, pharmacokinetics, **CCI** a central line or midline is **not** required by the study protocol, and should only be placed if clinically warranted;

- During dosing of the interventional product, the blood draws for pharmacokinetics should be done using the contralateral arm to the one being used for infusion of the study intervention. (When a simultaneous blood sample is required for safety assessments, **CCI** it is recommended to use the same venipuncture).

8.1. Efficacy Assessments

Not applicable.

8.2. Safety Assessments

Planned time points for all safety assessments are provided in the **SoA**. Unscheduled clinical laboratory measurements may be obtained at any time during the study to assess any perceived safety issues.

8.2.1. Physical Examinations

A complete physical examination will include, at a minimum, assessments of the cardiovascular, respiratory, gastrointestinal, and neurological systems. Height and weight will also be measured and recorded (height may be reported by participant if necessary) at screening only.

A targeted physical examination will include, at a minimum, assessments of the skin, lungs, cardiovascular system, and abdomen (liver and spleen).

Investigators should pay special attention to clinical signs related to previous serious illnesses.

8.2.2. Vital Signs

Temperature (Oral, Tympanic, Axillary or Temporal), pulse rate, respiratory rate, pulse oximetry/SpO₂, and blood pressure will be assessed. It is preferred that body temperature be collected using the same method for the same participant throughout the study.

Blood pressure and pulse rate measurements will be assessed in the supine position preferably with a completely automated device. Manual techniques will be used only if an automated device is not available.

Blood pressure and pulse rate measurements should be preceded by at least 5 minutes of rest for the participant in a quiet setting without distractions (eg, television, cell phones). Vital signs (to be taken before blood collection for laboratory tests) will include 1 pulse rate and 1 blood pressure measurements.

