1.3. Schedule of Activities

The SoA table provides an overview of the protocol visits and procedures. Refer to the [STUDY ASSESSMENTS AND PROCEDURES](#) section of the protocol for detailed information on each procedure and assessment required for compliance with the protocol.

The investigator may schedule visits (unplanned visits) in addition to those listed in the SoA table, in order to conduct evaluations or assessments required to protect the well-being of the participant.

PART 1: SAD (24-h infusion)

Visit Identifier	Screening Days -3 to 1	Day 1						End of Treatment Day 2	Follow-up 1 (Day 3)	Follow-up 2 (Day 6) ^k ±1 day Phone call where necessary	Follow-up 3 (Days 30-37) ^k Phone call where necessary	Early Termination
Planned Hours Post Start of Infusion		Pre-dose	0h	0.5h	2h	6h	12h	24h	48h			
ELIGIBILITY												
Informed consent	X											
Verify inclusion/exclusion criteria	X											
Demographics & Medical history	X											
Required Confinement		X	→	→	→	→	→	→	X			
PHYSICAL EXAMINATION & ECG & VITALS												
Complete physical examination	X							X				X
Targeted physical examination		X							X	X		
Supine Vital signs (temperature, pulse rate, blood pressure, respiratory rate)	X	X	X	X	X	X	X	X	X	X		X
Pulse oximetry/SpO ₂	X	X						X	X	X		X
Weight, Height	X											
12-Lead ECG ^a	X	X			X ^a	X ^a	X ^a	X	X			X
ECG Telemetry ^b	X	X	X	→	→	→	X					

Visit Identifier	Screening Days -3 to 1	Day 1						End of Treatment Day 2	Follow-up 1 (Day 3)	Follow-up 2 (Day 6) ^k ±1 day Phone call where necessary	Follow-up 3 (Days 30-37) ^k Phone call where necessary	Early Termination
Planned Hours Post Start of Infusion		Pre-dose	0h	0.5h	2h	6h	12h	24h	48h			
LABORATORY												
Hematology ^c	X	X				X		X	X	X		X
Blood chemistry ^c	X	X				X		X	X	X		X
Coagulation Panel (PT, aPTT, D-dimer) and Fibrinogen		X				X		X	X	X		X
Urinalysis ^c	X	X				X		X	X	X		X
FSH (post-menopausal females only) ^c	X											
Pregnancy test (WOCBP only)	X ^{c,d}									X ^d		
CCI [REDACTED]												
SARS-CoV-2 Viral load Assessments ^e	X	X				X		X	X	X		X
Plasma PD Biomarker Assessments ^g	X					X ^f		X	X	X		X
Serum PD Biomarker Assessments ^h	X					X ^f		X	X	X		X
Banked Biospecimen (Prep D1)	X					X ^f		X	X			X
Plasma Pharmacokinetics (PF-07304814 and PF-00835231)	X					X		X ⁱ	X			X
CCI [REDACTED]												
Urine Pharmacokinetics [REDACTED] (Cohort 2 only)		X ^j	X	→	→	→	→		X (36h)			
RANDOMIZATION												
STUDY INTERVENTION												

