3. OBJECTIVES, ESTIMANDS, AND ENDPOINTS

Objectives	Estimands	Endpoints
Primary:	Primary:	Primary:

To assess the safety and tolerability following single and multiple ascending doses of PF-07304814 in hospitalized participants with COVID-19.	N/A	
Frequency, severity, and causal relationship of TEAEs and withdrawals due to TEAEs (including infusion site reactions).Frequency and magnitude of abnormal laboratory findings.Changes from baseline in vital sign measurements, pulse oximetry/SpO₂, and 12-lead ECG parameters.
Secondary:	Secondary:	Secondary:

To evaluate the plasma PK of PF-07304814 and PF-00835231 and urinary PK of PF-00835231 following single ascending and multiple ascending doses in hospitalized participants with COVID-19.	N/A	Part 1: SAD 
PF-07304814 (prodrug) and PF-00835231 (active moiety) plasma PK: C₂₄ (end of infusion) and C₂₄ (dn).PF-00835231 urinary PK parameters: Ae, Ae%. Part 2: MAD 
PF-07304814 (prodrug) and PF-00835231 (active moiety) plasma PK: C₁₂₀ (end of infusion), C_{max}, C_{ss}, and t_{1/2}.
Tertiary/Exploratory:	Tertiary/Exploratory:	Tertiary/Exploratory:
■ [REDACTED]	C CI	■ [REDACTED]

Measurement of	N/A	
SARS-CoV-2 viral load (RT-PCR) and, if

Objectives	Estimands	Endpoints
SARS-CoV-2 viral load (by RT-PCR) and, if feasible, molecular analysis in nasopharyngeal swab and saliva samples over time.		feasible, molecular analysis in nasopharyngeal swab and saliva (at Screening, Days 1, 2, 3 and 6 for Part 1: SAD , and at Screening, Days 1, 3, 6, 7, 10, 14 and last follow-up for Part 2: MAD).

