### **3.1.5. Pulse Oximetry/SpO2**

Pulse oximetry/SpO2 will be taken at times detailed in the SoA given in the protocol.

The following pulse oximetry endpoints will be determined:

- Change from baseline in pulse oximetry/SpO2

Baseline will be defined as the last pre-dose measurement.

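### Part 1 schedules no SpO2 reading between pre-dose and 24 h, the end of infusion, although the other vital signs are taken at 0.5, 2, 6 and 12 h

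*Protocol*

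**What the plan says.** Protocol Section 3 names as a primary endpoint "Changes from baseline in vital sign measurements, pulse oximetry/SpO₂, and 12-lead ECG parameters".

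Section 8.2.2 (Vital Signs) includes oximetry in its list: "Temperature (Oral, Tympanic, Axillary or Temporal), pulse rate, respiratory rate, pulse oximetry". It gives no hours for any of these measurements. Section 8.2 sends the reader elsewhere for timing: "Planned time points for all safety assessments are provided in the" SoA.

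The Part 1 SoA (Section 1.3) has two separate rows. One is "Supine Vital signs (temperature, pulse rate, blood pressure, respiratory rate", without SpO2, marked at every column from screening to Day 6. The other is pulse oximetry/SpO2, marked at screening, pre-dose, 24 h, 48 h, Day 6 and early termination, with the cells from 0 to 12 h empty. In the Part 2 SoA the two rows carry the same marks at every visit.

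SAP 3.1.5 says that SpO2 "will be taken at times detailed in the SoA given in the protocol". SAP 6.1.5 summarises SpO2 by treatment and time and counts participants meeting the Appendix 1 category (below 94%), with unplanned readings included in that count. It splits these tables into three columns by oxygen use, judged from Days 2, 3 and 6 in Part 1 plus any unplanned readings from Day 2 to Day 6.

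**The concern.** The participants are hospitalised with a respiratory infection, and Part 1 is the first administration of the compound to humans. SpO2 is the primary-endpoint component closest to the disease, yet over the first 12 hours of infusion the schedule collects respiratory rate, pulse, blood pressure and temperature without it. The by-time SpO2 table will have nothing between pre-dose and 24 h, and SpO2 cannot be set beside the respiratory-rate and pulse values taken during that interval.

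The gap also reaches the sentinel step. The review committee clears the rest of a dose-escalating cohort on two participants, one of them on active drug. For that one participant the schedule yields a single on-infusion SpO2 value.

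No reason is given for separating the rows in Part 1 when they coincide in Part 2.

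**Working it through.** **Step 1. Count the scheduled readings.** The Part 1 SoA has 12 columns, and both rows fill the grid without ambiguity.

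| Time from start | Vital signs | SpO2 |
|---|---|---|
| Pre-dose | yes | yes |
| 0 h | yes | no |
| 0.5 h | yes | no |
| 2 h | yes | no |
| 6 h | yes | no |
| 12 h | yes | no |
| 24 h | yes | yes |
| 48 h | yes | yes |
| Day 6 | yes | yes |

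The 0 h column is the moment the infusion starts, so it is not an on-drug reading and is left out. Scheduled on-infusion readings per participant are then 5 for vital signs (0.5, 2, 6, 12 and 24 h) and 1 for SpO2 (24 h). With 6 active participants in a full cohort, that is 6 × 5 = 30 sets of vital signs against 6 × 1 = 6 SpO2 values.

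**Step 2. Set the gap against the rise in exposure.** Protocol Section 2.2.2.1 reports that in healthy participants (study C4611007) the active moiety was near its maximum from about 6 h and stayed there to the end of infusion. Its half-life was 2.25 h at 500 mg and 2.02 h at 700 mg. Section 4.3.3 says the half-life in patients was similar where it could be calculated. Assuming one compartment and rapid conversion of the prodrug, the fraction of steady state at time t under constant infusion is

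f(t) = 1 − 2^(−t / t½)

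| t | t½ = 2.25 h | t½ = 2.02 h |
|---|---|---|
| 0.5 h | 0.143 | 0.158 |
| 2 h | 0.460 | 0.497 |
| 6 h | 0.843 | 0.872 |
| 12 h | 0.975 | 0.984 |
| 24 h | 0.999 | 1.000 |

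This agrees with the reported near-maximum at about 6 h. It cuts both ways. The whole rise passes with no scheduled SpO2 value, but the 24 h value is taken at full plateau after the longest time on drug.

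**Step 3. Trace an early fall through the analysis.** Suppose SpO2 falls at 6 h, oxygen is given, and both have returned to their starting state before Day 2.

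- By-time table: no entry, because no SpO2 time is scheduled there.
- Below-94% count: an entry only if someone recorded an unplanned reading.
- Oxygen-use columns: Day 1 is not among the classifying days, so on the visible text the participant would count as never having received oxygen. Part of that sentence is redacted, so this reading is conditional.
- Adverse events: collected throughout, but Appendix 3 excludes expected signs and progression of the disease under study unless they are more severe than expected.

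**The case against.** The strongest reply is that the documents contain no contradiction. A reader might infer that Section 8.2.2 requires SpO2 at 0.5, 2, 6 and 12 h and that the SoA drops it. That inference fails: Section 8.2.2 sets no times, Section 8.2 leaves timing to the SoA, and the SoA row carrying those hours excludes SpO2. The endpoint wording and the SAP also treat SpO2 as an item apart from the vital signs. What remains is inconsistent grouping and a sparse schedule.

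A reader might also infer that Part 1 will hold no SpO2 data from the build-up. The documents do not support this either. Protocol Section 1.3 allows extra assessments for participant protection, unplanned readings enter the below-94% count, and adverse event monitoring is continuous. The accurate statement is that no reading is scheduled. Unplanned values are taken when someone has a reason to look, so they can show events but cannot give a comparable profile by treatment.

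Two further points have force. In Part 2 the first SpO2 after the start of infusion is also at 24 h, so a late first reading is not peculiar to Part 1. In Part 2, however, the vital signs follow the same schedule. And the 24 h reading samples sustained plateau exposure, so a fall that persists would be caught. Only a transient early fall is at risk, and the available text names no such specific risk.

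Finally, participants had already been dosed in Cohorts 1 and 3 by Amendment 4, so a change would leave different schedules within small cohorts. That stands as a cost.

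**Conclusion.** The gap is real and modest. One component of the primary safety endpoint has 1 scheduled on-infusion value per Part 1 participant against 5 for the other vital signs, and none before 24 h. It limits what Part 1 can say about early, reversible changes in SpO2. It does not undermine the end-of-infusion comparison, and no hypothesis test depends on it, because the safety analysis is descriptive.

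The conclusion assumes that the 24 h SpO2 is taken at or just before the end of infusion; the SoA gives such a window for PK and ECG but not for SpO2. The exposure timing comes from healthy participants and a one-compartment approximation. Whether oxygen support is captured on Day 1 cannot be settled, since parts of the SoA and of SAP 6.1.5 are redacted. This is a cheap improvement rather than a correction of an error.

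**What to change.** For participants still to be dosed in Part 1:

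- Mark the SpO2 row of the Part 1 SoA at 0.5, 2, 6 and 12 h, and record oxygen support with each reading.
- Make Section 8.2.2 and the SoA treat SpO2 the same way, either as a vital sign or as a separate item.
- Add the four times to the by-time and below-94% summaries in SAP 6.1.5.
- Include Day 1 in the SAP 6.1.5 oxygen-use classification. Otherwise the new Day 1 values would be sorted into columns defined only by later oxygen use.

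For participants already dosed, list any unplanned Day 1 SpO2 values and state in the report that none were scheduled between pre-dose and 24 h. If Part 1 dosing is complete, only this paragraph applies, together with the Day 1 classification where the data exist.

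The cost is four non-invasive bedside readings per participant (4 × 8 = 32 in a full cohort), at times when staff already take vital signs, plus SoA, CRF and SAP edits. The schedule would be mixed across Part 1 cohorts, so the early time points should show the number of participants contributing and should not be read across cohorts as if complete.
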